6.5. Subset Analyses

There is no planned subset analysis for this study.

6.6. Baseline and Other Summaries and Analyses

6.6.1. Baseline Summaries

Descriptive summary including n, mean, SD, median, minimum, and maximum will be presented for continuous baseline variables. Frequency and percentage will be provided for categorical baseline variables. The following baseline data and disease characteristics will be summarized, if data permits.

- Demographic data: Age, race, ethnicity, proportion of Ashkenazi Jewish descent (via number of grandparents) will be summarized by gender at birth and ‘All Participants’ in accordance with the Pfizer reporting standards.
- Primary diagnosis: Type of GD, method of diagnosis and symptoms presented at the diagnosis will be summarized.
- Medical history: General MH will be summarized by SOC and PT according to MedDRA dictionary in the latest available version.

6.6.2. Study Conduct and Participant Disposition

Participant evaluation groups will show end of study participant disposition and will show which participants were analyzed for efficacy and safety (adverse events and laboratory data).

Frequency counts and percentage will be reported for participant discontinuation(s), temporary discontinuation(s) or dose reduction due to adverse events and reasons for discontinuation.

Data will be reported in accordance with the Pfizer reporting standards.

6.6.3. Study Treatment Exposure

Taliglucerase dosing (study drug administration schedule) will be listed for each participant. Dose will be descriptively summarized as n, median, minimum, maximum, mean and SD.

6.6.4. Concomitant Medications and Nondrug Treatments

The concomitant medication(s) and non-drug treatment(s) will be provided in the listings.

6.7. Safety Summaries and Analyses

All the safety data will be summarized descriptively through the appropriate data tabulations in safety population (defined in [Section 4](#)) according to Pfizer Safety Rulebook and CDISC standards analyses, to evaluate any potential risk associated with the safety and toleration of administering taliglucerase alfa in Type 3 GD patients.

6.7.1. Adverse Events

Treatment-emergent adverse events (TEAE) will be summarized with counts and percentage for safety population (defined in [Section 4](#)) according to Pfizer CDISC standard. All adverse events will be reported in a data listing.

In addition to the system organ class (SOC) and preferred term (PT) defined in the live MedDRA version at the final reporting stage, an additional SOC of hypersensitivity reactions will be summarized using frequency and percentage for each preferred term, including but not limited to:

- Early clinical signs: sensation of warmth and itching, feelings of anxiety or panic;
- Moderate clinical signs: pruritus, flushing, urticaria, chest discomfort, mild hypotension;
- Progressive clinical signs: erythematous or massive urticarial rash;
- Severe clinical signs: hypotension, bronchospasm (wheezing), laryngeal edema (dyspnea, stridor, aphonia, drooling), arrhythmias.

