5 WARNINGS AND PRECAUTIONS

5.1 Hypersensitivity Reactions Including Anaphylaxis

Serious hypersensitivity reactions, including anaphylaxis, have occurred in some patients treated with ELELYSO. In clinical trials, 2 of 72 (3%) patients treated with ELELYSO experienced signs and symptoms consistent with anaphylaxis. Signs and symptoms of these patients included urticaria, hypotension, flushing, wheezing, chest tightness, nausea, vomiting, and dizziness. These reactions occurred during ELELYSO infusion.

In clinical trials with ELELYSO, 21 of 72 (29%) patients experienced hypersensitivity reactions, including anaphylaxis. Signs and symptoms of hypersensitivity reactions included pruritus, angioedema, flushing, erythema, rash, nausea, vomiting, cough, chest tightness, and throat irritation. These reactions have occurred up to 3 hours after the start of infusion [see *Adverse Reactions (6.1)*].

Due to the potential for anaphylaxis, appropriate medical support should be readily available when ELELYSO is administered. Observe patients closely for an appropriate period of time after administration of ELELYSO, taking into account the time to onset of anaphylaxis seen in clinical trials. Inform patients of the signs and symptoms of anaphylaxis, and instruct them to seek immediate medical care should signs and symptoms occur. If anaphylaxis occurs, ELELYSO should be immediately discontinued, and appropriate medical treatment should be initiated. Management of hypersensitivity reactions should be based on the severity of the reaction and include slowing or temporary interruption of the infusion and/or administration of antihistamines, antipyretics, and/or corticosteroids for mild reactions. Pretreatment with antihistamines and/or corticosteroids may prevent subsequent hypersensitivity reactions. Patients were not routinely premedicated prior to infusion of ELELYSO during clinical studies. If severe hypersensitivity reactions occur, immediately stop the infusion of ELELYSO and initiate appropriate treatment.

Consider the risks and benefits of re-administering ELELYSO in patients who have experienced a severe reaction associated with ELELYSO. Caution should be exercised upon rechallenge, and appropriate medical support should be readily available [see *Adverse Reactions (6.3)*].

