6 ADVERSE REACTIONS

6.1 Clinical Trials Experience

Because clinical trials are conducted under widely varying conditions, adverse reaction rates observed in the clinical trials of a drug cannot be directly compared to rates in the clinical trials of another drug and may not reflect the rates observed in practice.

Clinical Trials of ELELYSO as Initial Therapy

• Clinical Trial in Patients 19 Years and Older

The safety of ELELYSO at dosages of either 30 units/kg (n=16) or 60 units/kg (n=16) every other week was assessed in 32 adult treatment-naïve patients (aged 19 to 74 years) with Type 1 Gaucher disease in a 9-month double-blind, randomized clinical trial.

Table 1: Adverse Reactions in ≥5% of Treatment-Naïve Adult Patients Treated with ELELYSO

Preferred Term	Treatment-Naïve Adults (N=32) n (%)
Headache	6 (19)
Arthralgia	4 (13)
Fatigue	3 (9)
Nausea	3 (9)
Dizziness	3 (9)
Abdominal pain	2 (6)
Pruritus	2 (6)
Flushing	2 (6)
Vomiting	2 (6)
Urticaria	2 (6)

• Clinical Trial in Patients 16 Years and Younger

The safety of ELELYSO at dosages of either 30 units/kg (n=4) or 60 units/kg (n=5) every other week was assessed in 9 pediatric treatment-naïve patients (aged 2 to 13 years) with Type 1 Gaucher disease in a 12-month randomized clinical trial.

The most common adverse reaction (≥10%) was vomiting, which occurred in 4 of 9 patients. Two patients developed hypersensitivity reactions; one patient experienced severe vomiting and gastrointestinal inflammation, and 1 experienced mild throat irritation and chest discomfort. Both patients responded to treatment with antihistamines and continued ELELYSO treatment.

Clinical Trial in Patients Switching from Imiglucerase Treatment to ELELYSO

The safety of ELELYSO was assessed in 31 patients (26 adult and 5 pediatric patients), ages 6 to 66 years old, with Type 1 Gaucher disease who had previously been receiving treatment with imiglucerase for a minimum of 2 years. ELELYSO was administered for 9 months at the same number of units as each patient's previous imiglucerase dose.

Table 2: Adverse Reactions in ≥10% of Patients Switched from Imiglucerase to ELELYSO (after 9 months on treatment)

Preferred Term	Patients Switched from Imiglucerase (N=31; 26 adults and 5 children) n (%)
Arthralgia	4 (13)
Headache	4 (13)
Pain in extremity	3 (10)

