8.4 Pediatric Use

The use of ELELYSO for treatment of pediatric patients with Type 1 Gaucher disease is supported by evidence of effectiveness from adequate and well-controlled trials of ELELYSO in adults, with additional pharmacodynamic data from 5 pediatric patients and pharmacokinetic data from 9 pediatric patients who participated in clinical trials [see Clinical Studies (14.1, 14.2), Clinical Pharmacology (12.3)]. Data from 14 pediatric patients were included in the safety evaluation [see Adverse Reactions (6.1)]. There are insufficient data to inform dosing in patients less than 4 years of age.

Pediatric patients experienced a higher frequency of vomiting during ELELYSO treatment (4 of 9 treatment-naïve patients) than adult patients, and this may be a symptom of hypersensitivity reaction. The frequencies of other adverse reactions were similar between pediatric and adult patients [see Adverse Reactions (6.1)].

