14.3 Appendix 3: Taliglucerase Alfa Hypersensitivity Evaluation and Treatment Algorithm

During and after infusion of taliglucerase alfa, the following algorithm will be followed to monitor and manage the occurrence of hypersensitivity, anaphylaxis, or anaphylactoid reactions.

Clinical Signs

Early

- Sensations of warmth and itching
- Feelings of anxiety or panic

Moderate

- Pruritus
- Flushing
- Urticaria
- Chest discomfort
- Mild hypotension

Progressive

- Erythematous or massive urticarial rash
- Edema of face, neck, soft tissues

Severe

- Hypotension
- Bronchospasm (wheezing)
- Laryngeal edema (dyspnea, stridor, aphonia, drooling)
- Arrhythmias

Treatment Algorithm

With the onset of any of the above clinical signs, immediately discontinue study medication administration and initiate the following monitoring:

- Continuous electrocardiographic monitoring
- Continuous pulse oximetry
- Measure blood pressure every 5 minutes
- Perform chest auscultation every 5 minutes

- Blood samples need to be collected for Tryptase (29-33) and antibodies. Tryptase samples need to be withdrawn at:
 - 1st sample taken 0.25-3 hours after onset of symptoms
 - 2nd sample taken between 3-6 hours
 - 3rd sample taken 24-48 hours to verify the return to baseline

In the case of progressive or severe hypersensitivity, treat appropriately and withdraw the subject from the study. Treat as detailed below.

Urticaria or edema of the face, neck, or soft tissues

- Epinephrine 1:1000 solution, 0.5 mL subcutaneously, repeat as needed every 5-10 minutes
- Antihistamines
- Corticosteroids

Hypotension (systolic blood pressure (SBP) \leq 90 mmHg)

- Isotonic sodium chloride solution, 1 L every 30 minutes as needed to maintain SBP >90 mmHg
- Epinephrine 1:10,000 solution given IV at 1 μ g/minute initially, then 2-10 μ g/minute to maintain SBP >90 mmHg
- Norepinephrine 4 mg in 1 L 5% dextrose in water given IV at 2-12 μ g/minute to maintain SBP >90 mmHg
- Glucagon 1 mg in 1 L 5% dextrose in water given IV at 5-15 μ g/minute for refractory hypotension

Bronchospasm

- Oxygen by face mask at 6-8 L/minute to maintain oxygen saturation at $>90\%$
- Epinephrine 1:1000 solution, 0.5 mL subcutaneously
- Albuterol 0.5 mL of 0.5% solution in 2.5 mL of sterile saline every 15 minutes up to three doses
- Inhaled beta-agonists
- Corticosteroids

Laryngeal edema

- Epinephrine 1:1000 solution, 0.5 mL subcutaneously, repeat as needed every 5 to 10 minutes
- Corticosteroids

Premedication

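### The hypersensitivity category in SAP 6.7.1 has no infusion window or relatedness condition and an incomplete, open term list, so the reported rate could be over- or under-counted

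*SAP*

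**What the plan says.** SAP 6.7.1 states that, beyond the usual system organ classes, "an additional SOC of hypersensitivity reactions will be summarized using frequency and percentage for each preferred term, including but not limited to" four tiers of signs: early, moderate, progressive and severe. The third tier reads in full: "Progressive clinical signs: erythematous or massive urticarial rash". The category sits within the TEAE summary. SAP 3.5.1 defines TEAEs as events that start or worsen from the first dose on, with reporting to 30 days after the final dose. Onset and relatedness are collected, but neither section makes the interval from infusion to onset, or the investigator's causality assessment, a condition for entering the category.

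The tiers match protocol Appendix 14.3 item for item, with one exception: the progressive tier there has a second item, "Edema of face, neck, soft tissues", which the SAP leaves out. The appendix also puts its list in an infusion setting, though without an upper time limit: "During and after infusion of taliglucerase alfa, the following algorithm will be followed to monitor and manage the occurrence of hypersensitivity".

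The US label, attached as Appendix 14.1, gives a different set of signs in its section 5.1: "pruritus, angioedema, flushing, erythema, rash, nausea, vomiting, cough, chest tightness, and throat irritation". On timing it says "These reactions have occurred up to 3 hours after the start of infusion". On vomiting in children, label section 8.4 says "this may be a symptom of hypersensitivity reaction".

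**The concern.** Hypersensitivity is the labelled warning for this drug, and this is the only adverse event grouping for which the SAP builds its own category. Two features leave its content unsettled.

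First, several listed terms are non-specific: anxiety, pruritus, dyspnea, drooling, arrhythmia. In Appendix 14.3 they are read in the setting of an infusion. Moved into a TEAE table without that setting, they count as reactions months after enrolment and days away from any dose. Dyspnea and drooling stand in brackets after laryngeal edema, and the SAP does not say whether they count on their own. The trial has one arm, so there is no control rate to show the background.

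Second, the list is open. One source item is missing, and the label signs that are absent can be added but need not be. In an open-label study that choice would be made after the events are known.

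At stake is a descriptive safety rate in a small study. No efficacy result or formal test depends on it.

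**Working it through.** **1. The stated rates.** The label's section 5.1 gives the only overall figures that bear on the point. 21/72 = 29.2% (stated 29%) and 2/72 = 2.8% (stated 3%). Both reproduce.

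**2. The lists side by side.** Only the rows relevant here:

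| Sign | SAP 6.7.1 | Appendix 14.3 | Label 5.1 |
|---|---|---|---|
| Rash | yes | yes | yes |
| Chest discomfort or tightness | yes | yes | yes |
| Facial, neck or soft-tissue edema | no | yes | angioedema |
| Nausea | no | no | yes |
| Vomiting | no | no | yes |
| Cough | no | no | yes |
| Throat irritation | no | no | yes |

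The edema gap is in the SAP only. The last four signs are in neither of the trial's own lists. Anaphylaxis as a recorded diagnosis is not a named term in the SAP list either.

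**3. The time over which a listed term counts.** Week 0 to Week 52 plus 30 days: 52 × 7 + 30 = 394 days. Visits 1 to 27 give 27 infusion days: 27/394 = 6.9% of the period. The label's 3 hours gives 27 × 3 = 81 of 394 × 24 = 9,456 hours, or 0.9%. These are shares of calendar time. They show how loosely the category is tied to infusion; they are not error rates.

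**4. Weight of one subject.** 1/15 = 6.7% and 1/9 = 11.1%, using the planned maximum enrolment and the evaluable sample size.

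**5. How far the definition can move a rate (illustration).** The label's pediatric trial had 9 treatment-naïve children and 2 reactors: "one patient experienced severe vomiting and gastrointestinal inflammation, and 1 experienced mild throat irritation and chest discomfort". Four of the 9 vomited (label 8.4).

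- Named SAP signs only: the chest discomfort case matches and the vomiting case does not, so 1/9 = 11% (exact 95% CI 0.3 to 48.2%).
- As reported: 2/9 = 22% (2.8 to 60.0%).
- Vomiting added with no window and no relatedness rule: 4/9 to 5/9 = 44 to 56%, depending on whether the chest discomfort case was one of the four who vomited.

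Adding terms without a timing or relatedness rule can thus overshoot as easily as leaving them out undershoots.

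**6. Background events.** The documents give no rate. Assume 0.1 to 1.0 unrelated listed events per person-year (an assumption, not a figure from the plan). Expected subjects flagged by chance = N × [1 − exp(−rate × T)].

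- No window, T = 394/365.25 = 1.079 years: 0.9 to 5.9 of 9, or 1.5 to 9.9 of 15.
- Infusion day only, T = 27/365.25 = 0.074 years: 0.07 to 0.64 of 9, or 0.11 to 1.07 of 15.

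The first range is too wide to give a magnitude. It shows only that a same-day flag removes most chance events at any rate in the range.

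**The case against.** A reader might infer that the rate would certainly be wrong in both directions, with 11% reported where 22% is true. The documents do not support that. The list is open, so unlisted terms may enter. Protocol 8.2.1.1 asks for diagnoses rather than signs where a diagnosis is available, so a vomiting reaction recorded as hypersensitivity could be counted. The 1/9 is one hypothetical built on brief case descriptions.

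A reader might also take 0.9% of the hours as the size of the over-count. It is not an event rate.

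Nor can the point rest on comparability with the label's 29% or 2/9. The label reports observed onset but not the term list or window by which cases were counted, so fixing the SAP would not make the rates comparable. The SAP plans no such comparison.

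There is real mitigation elsewhere. Results are shown by preferred term, all events are listed, and protocol 10.3.5.1 adds a summary by attribution and narratives for significant events. Omitted terms still appear in the ordinary tables, so they are misclassified rather than lost. SAP 6.7 and 6.7.1 also defer to sponsor reporting standards that are not in the documents.

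Lastly, one might read a clinical gap into Appendix 14.3 because its algorithm does not name vomiting. Appendix 14.2 handles infusion symptoms separately with an open list and toxicity grades. All that can be said is that the sign lists differ.

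What stands: none of this supplies a window or a relatedness condition for the category, restores the edema item, or fixes the terms in advance. Protocol 8.2.1.1 ties TEAEs to a period of residual drug effect but gives no length, and SAP 3.5.1 does not carry it over.

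**Conclusion.** The concern holds as a gap in pre-specification. As written, the category counts non-specific terms across about 394 days, omits an item its own source contains, and leaves the label's other signs to later choice. The rate could be over- or under-counted. Each reclassified subject moves it by 7 to 11 percentage points, assuming 9 to 15 treated subjects. The over-count cannot be sized because no background rate is given, and the pediatric figures are an illustration only. The effect is confined to a descriptive safety table, but that table is the natural place to look for the drug's main warning, and the repair is cheap.

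**What to change.** In SAP 6.7.1, before database lock:

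- Restore the edema item and close the term list. Include investigator-recorded diagnoses of hypersensitivity or anaphylaxis and the signs in label section 5.1.
- Derive a flag for onset on the day of an infusion. This needs only the event start dates in protocol 8.2.1.2 and the dosing dates listed under SAP 6.6.3. A window in hours would need clock times: SAP 3.5.1 mentions time of onset, the protocol only dates, so the two would first have to be reconciled.
- Report the number of subjects with at least one flagged event, overall and by investigator relatedness, beside the same count without the window.

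The cost is one derived flag and a slightly larger table. A same-day window alone may miss delayed reactions and may catch unrelated vomiting on an infusion day (4 of 9 children vomited in the label's trial, 2 of 9 were reactors). That is why the unwindowed and by-relatedness counts should be shown too.

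Separately, the sponsor should reconcile the sign list in Appendix 14.3 with sections 5.1 and 8.4 of the label in Appendix 14.1. No clinical rule is proposed here.

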6.7.2. Laboratory Data

Laboratory data will be presented in accordance with the Pfizer CDISC reporting standards.

6.7.3. Vital Signs

All vital sign data will be listed by participant and visit.

Though vital signs will be collected during each infusion visit per standard of care, only vital sign collected at the baseline, Month 3, 6, 9 and 12 will be summarized descriptively. Absolute values, change from baseline and percent change from baseline for vital sign data will be summarized using n, mean, SD, median and range.

6.7.4. Physical Examination

Physical examination and neurologic assessment data will be listed only by participant and visit.

7. INTERIM ANALYSES

There is no planned interim analysis in this study.

9. APPENDICES

Appendix 1. Summary of Efficacy Analyses

Endpoint	Analysis Type	Population	Data Inclusion and Rules for Handling Intercurrent Events and Missing Data	Analysis Model
Percent change from baseline to Month 12 in spleen volume MN measured by MRI	Summary	Evaluable (FAS), PP	observed data at each visit	N/A
	Main analysis	Evaluable (FAS)	Month 12 or data from early termination assessment and baseline	Wilcoxon signed rank test (exact p-value), median %change
	Sensitivity analysis	PP	completed both Month 12 and baseline without missing data imputation	Wilcoxon signed rank test (exact p-value), median %change
Responder rate in spleen volume reduction measured by MRI	Supplementary analysis	Evaluable (FAS)	Month 12 or data from early termination assessment and baseline	Clopper-Pearson CI
Percent change from baseline to Month 12 in liver volume MN measured by MRI	Summary	Evaluable (FAS)	observed data at each visit	N/A
	Main analysis	Evaluable (FAS)	Month 12 or data from early termination assessment and baseline	Wilcoxon signed rank test (exact p-value), median %change
Percent change from baseline in hemoglobin	Summary	Evaluable (FAS)	observed data at each visit (baseline, Month 3, 6, 9, 12)	N/A
	Main analysis	Evaluable (FAS)	Month 12 or data from early termination assessment and baseline	Wilcoxon signed rank test (exact p-value), median %change
Percent change from baseline in platelet	Summary	Evaluable (FAS)	observed data at each visit (baseline, Month 3, 6, 9, 12)	N/A
	Main analysis	Evaluable (FAS)	Month 12 or data from early termination assessment and baseline	Wilcoxon signed rank test (exact p-value), median %change
Percent change from baseline in Lyso-Gb1	Summary	Evaluable (FAS)	observed data at each visit (baseline, Month 3, 6, 9, 12)	N/A
	Main analysis	Evaluable (FAS)	Month 12 or data from early termination assessment and baseline	Wilcoxon signed rank test (exact p-value), median %change

Endpoint	Analysis Type	Population	Data Inclusion and Rules for Handling Intercurrent Events and Missing Data	Analysis Model
Percent change from baseline in chitotriosidase	Summary	Evaluable (FAS)	observed data at each visit (baseline, Month 3, 6, 9, 12)	N/A
	Main analysis	Evaluable (FAS)	Month 12 or data from early termination assessment and baseline	Wilcoxon signed rank test (exact p-value), median %change
Change from baseline in height SDS	Summary	Evaluable (FAS)	observed data at each visit	N/A
Change from baseline in weight SDS	Summary	Evaluable (FAS)	observed data at each visit	N/A
Change from baseline in bone assessment	Summary	Evaluable (FAS)	observed data at each visit	N/A
Percent change from baseline to Month 12 in spleen volume MN measured by ultrasound	Summary	Evaluable (FAS)	observed data at each visit	N/A
Percent change from baseline to Month 12 in liver volume MN measured by ultrasound	Summary	Evaluable (FAS)	observed data at each visit	N/A
Change from baseline in VAS fatigue score	Summary	Evaluable (FAS)	observed data at each visit	N/A
Tanner stage	Summary	Evaluable (FAS)	observed data at each visit	N/A
Change from baseline in total score from mSST	Summary	Evaluable (FAS)	observed data at each visit	N/A
Anti-taliglucerase antibodies	Summary	Evaluable (FAS)	observed data at each visit	N/A

